2.2 Violations and deviations

We have not identified any important protocol deviations in this study to date. To our knowledge, no patients were erroneously randomized (in that they did not actually meet inclusion or exclusion criteria at the time of randomization). In other words, at the time the assignment was actually performed in Oct 2016 and Dec 2016, all patients were eligible for the study.

However, once the database lockout for follow-up outcomes is complete (late March 2018), Horizon will be sharing the full data, including prescription claims, medical claims, enrolment files, and laboratory values, to the [REDACTED] investigators for study analysis. Once these data are cleaned and the analytic dataset is generated, it is possible that a few patients may appear to have been erroneously randomized because there may have been new lab values provided to Horizon that were not actually available to Horizon at the time the allocation was performed. In addition, because of the minor lag between pulling the data, evaluating eligibility in insurer claims data, and the subsequent randomization done by Horizon, it is possible that a small percentage of individuals may have terminated their medical or prescription drug benefits and could no longer be eligible.

Based on prior studies of insurance trials conducted in claims data, we anticipate that no more than 5% of patients may be subject to any protocol deviations related to insurance data lag or adjudication.^{4,5,9} Moreover, we do not expect that there will be any differential deviations between the two study arms, so the study results should be unbiased. Regardless, patients who are found to have not met these enrolment criteria once the data is received will not be included in either of the Analysis Sets. Similarly, in the rare case that patients are found to have randomized multiple times or if there were any other unanticipated deviations, they will not be included in the Analysis Sets. We do not expect any of these potential deviations to affect the validity of the study results as they are not expected to be differential between the study arms.⁹

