1.3 Number of subjects

In total, 1,400 subjects were randomized in a 1:1 ratio to the intervention or control group. Our study was designed to be sufficiently powered to detect small but clinically meaningful changes in the primary outcome of HbA1c change.

We considered the following assumptions in the power calculations. Assuming that 30% of study subjects in the intervention arm agree to participate in the intervention, we randomized 700 individuals

to each of the intervention and control groups in order to achieve 80% power to detect an average change in HbA1c of 0.5% between the intervention and control groups at an alpha threshold of 0.05 with a HbA1c standard deviation=1.9 (the most commonly cited value in the literature for HbA1c), accounting for 25% rate of loss-to-follow-up.^{1,2} We used Proc Power in SAS 9.4 (Cary, NC) using a t-test and adjusted the sample size to account for the reach rate. Because patients may change insurance, in particular at the end of the calendar year, we accounted for a rate of non-differential loss-to-follow-up of 25% rate. There may also be patients who do not have follow-up HbA1cs, despite restricting to patients whose providers have at-risk contracts with Horizon Blue Cross Blue Shield. As described later in Section 3, we will use multiple imputation methods to account for patients with no follow-up HbA1c values. In addition, this proportion of patients who agree to participate in this intervention has been observed in prior studies that have used a similar approach.²⁵ Finally, the proposed difference of HbA1c of 0.5% is the level that clinical guidelines consider to be a clinically meaningful difference in glycemic control. This HbA1c difference has also been observed in prior work with clinical pharmacists.⁸ Because the primary outcome is HbA1c change, we expect to see clinically meaningful differences in these levels within the 11 to 12-month follow-up period.^{3,4}

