3. PRIMARY AND SECONDARY VARIABLES

3.1 Primary outcome (mean change in glycemetic control):

The primary outcome of interest will be the pre- to post-intervention change in mean HbA1c levels to the end of the 12-month follow-up period. Follow-up will begin from the date of treatment group assignment. The data for this outcome will be based on laboratory information that Horizon Blue Cross Blue Shield of New Jersey receives from over 200 patient-centered medical homes and other population health programs used for quality improvement monitoring. This laboratory information will be used to measure the change in HbA1c levels at the end of follow-up. In specific, the HbA1c result recorded closest to the 12-month end of follow-up as provided in the laboratory data will be used for the primary analysis.

For subjects with missing outcome data, multiple imputation will be used to impute missing follow-up values to calculate the change in HbA1c levels.¹⁰ Of note, all patients by definition for inclusion in the study will have baseline HbA1c values. This imputation approach is used to generate multiple results for missing values based on the underlying distribution of the available data. We will test the robustness of this approach with sensitivity analyses that use alternative methods of handling missing data, including complete case analysis.

This outcome will be analysed formally. We will also explore any potential differences in effectiveness by the pharmacist delivering the intervention.

3.2 Secondary outcome (proportion achieving glycemic control):

The secondary glycemic outcome will include the proportion of patients achieving optimal glycemic control. Optimal glycemic control will be defined as the proportion of patients who achieved an HbA1c result <8.0% in the 12-month follow-up period. This conservative threshold is based on the minimum threshold that nearly all patients should achieve based on guidelines from the American Diabetes Association (ADA) and quality measures used to assess the performance of health plans.^{11,12} In specific, we will use the laboratory information provided to Horizon and will use the HbA1c result recorded closest to the 12-month end of follow-up for the primary analysis.

For subjects with missing outcome data, we will use multiple imputation to impute missing follow-up values to calculate the proportion of patients who achieved this threshold.

This outcome will be analysed formally.

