4.2 Analysis methods

4.2.1 Primary objective (Effectiveness of intervention):

Baseline characteristics:

We will measure key baseline characteristics in the 12-months prior to randomization in the pharmacy and medical claims data and enrolment files. These characteristics will include sociodemographic characteristics, such as age and sex, which will be measured in the enrolment files. We will also measure baseline clinical characteristics such as the presence of coronary artery disease, chronic obstructive pulmonary disease, asthma, hypertension, hyperlipidemia, congestive heart failure, depression, liver disease, chronic kidney disease, osteoporosis and prior macrovascular complications. These will be measured in medical claims files using ICD-10 codes. We will also measure the type of oral glucose-lowering agent used in the baseline period (e.g., medical class), average PDC at baseline, and whether or not the medication is branded. We will also measure patients' latest copayments for oral glucose-lowering agents in the baseline period. Finally, we will also measure baseline healthcare resource utilization variables as characteristics including the number of days hospitalized and the number of physician office visits.

We will report, in tabular format, the means and frequencies of baseline characteristics prior to assignment separately for patients in the intervention and control groups and compare these values using t-tests, chi-square tests, and their non-parametric analogues, as appropriate. We will provide absolute standardized differences between the two treatment groups.

Primary analyses:

Primary outcome (change in HbA1c): In the primary analysis, the primary outcome, mean change in glycemic control, will be compared using generalized estimating equations with an identity link function (as a continuous variable) and normally distributed errors within the imputed full analysis set, as described above. Data will be presented as the unadjusted absolute difference in the change in HbA1c between the groups along with 95% confidence intervals.

Secondary outcome (proportion achieving glycemic control)

1) *Proportion of patients achieving optimal glycemic control* (defined by HbA1c < 8): This outcome will be compared using generalized estimating equations with a logit link and binary distributed errors. Data will be presented as the unadjusted odds ratio for optimal glycemic control between the groups along with 95% confidence intervals.

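### Patients were assigned in two rounds (October and December 2016), but round appears in neither the primary HbA1c model nor a specified imputation model: a minor gap that is cheap to close

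*SAP*

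**What the plan says.** - **Assignment.** SAP 2.2 discusses eligibility "at the time the assignment was actually performed in Oct 2016 and Dec 2016". SAP 1.3 gives only the overall ratio: "1,400 subjects were randomized in a 1:1 ratio to the intervention or control group". Round sizes, stratification and the ratio within each round are not stated. Protocol 9.3 planned recruitment within Quarter 3 of 2016 and does not mention rounds.
- **Follow-up and outcome.** SAP 3.1: "Follow-up will begin from the date of treatment group assignment". The value analysed is "the HbA1c result recorded closest to the 12-month end of follow-up", with no window around month 12.
- **Loss.** SAP 1.3 assumes 25% non-differential loss and explains when it occurs: "Because patients may change insurance, in particular at the end of the calendar year".
- **Primary model.** In SAP 4.2.1 the outcome "will be compared using generalized estimating equations with an identity link function (as a continuous variable) and normally distributed errors". No covariate is listed, and "Data will be presented as the unadjusted absolute difference in the change in HbA1c between the groups".
- **Missing data.** SAP 3.1: "multiple imputation will be used to impute missing follow-up values to calculate the change in HbA1c levels". No imputation variable is listed.
- **Adjustment.** SAP 4.2.1 repeats the analyses with covariates if baseline characteristics judged to be confounders show a standardised difference above 0.1. Round and assignment date are not among the characteristics it lists.

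**The concern.** When patients are assigned at two separate times, the usual practice is to account for assignment time in the analysis. If the ratio differed by round, or if round mix came to differ between arms after loss, any difference in HbA1c change between rounds would enter the treatment contrast.

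Round also matters for the missing data. A year-end leaver from the October round has had two to three months in which an HbA1c could be recorded. With no window, that early value can stand as the one nearest month 12. A December leaver has had at most one month and will more often be imputed. A variable that plausibly predicts whether a value is observed belongs in the imputation model. At stake is how credible the missing-at-random assumption is, plus a little precision.

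**Working it through.** **1. The plan's own figure.** Protocol Table 5 uses difference 0.5, SD 1.9, two-sided alpha 0.05 and power 0.80. The t-test solution is 227.6, so 228 as stated. Then 228 × 1.03 / (1 − 0.25) / 0.45 = 695.8, against 696 stated. This point does not dispute that figure; 228 is reused in step 5.

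**2. Calendar.** Days from assignment to year-end:

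| Assigned | to 31 Dec 2016 | to 31 Dec 2017 |
|---|---|---|
| 1 Oct 2016 | 91 (3.0 months) | 456 (15.0) |
| 31 Oct 2016 | 61 (2.0) | 426 (14.0) |
| 1 Dec 2016 | 30 (1.0) | 395 (13.0) |
| 31 Dec 2016 | 0 (0.0) | 365 (12.0) |

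Each round meets one year-end early in follow-up, at different times. The second falls at or after month 12 for both rounds.

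**3. Bias from omitting round.** Bias = g × d. Here g is the difference between rounds in mean HbA1c change, and d is the difference between arms in the share of December patients among those analysed. The documents give neither, so both are assumptions.

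- *Allocation 1:1 within rounds, same loss in both arms:* d = 0, bias 0.
- *Arms differ in round mix by 5–10 points, g = 0.25–0.5:* 0.05 × 0.25 = 0.0125; 0.10 × 0.5 = 0.05.
- *Equal rounds, loss crossed between arms* (October/December loss of 15%/30% in one arm and 30%/15% in the other; 15–30% is the loss range in Protocol Table 5). December share: 0.5 × 0.70 / (0.5 × 0.70 + 0.5 × 0.85) = 0.4516 in one arm and 0.5 × 0.85 / 0.775 = 0.5484 in the other, so d = 0.0968. For g = 0.1, 0.3, 0.5 the bias is 0.0097, 0.029, 0.048.
- *Milder difference* (25%/30% against 25%/25%): d = 0.0172, bias 0.0017 to 0.0086 for g = 0.1 to 0.5.

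Against the 0.5 target, 0.0097/0.5 = 1.9% and 0.05/0.5 = 10%.

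**4. Imputation check.** Simulated normal multiple imputation with 700 per arm, equal rounds, SD 1.9, 600 replicates and 10 imputations. Arm was always in the imputation model; round and round-by-arm were left out or included. Bias in the treatment difference:

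| g | Same loss, round out | Same loss, round in | Crossed loss, round out | Crossed loss, round in |
|---|---|---|---|---|
| 0.1 | −0.001 | −0.001 | −0.015 | −0.005 |
| 0.3 | 0.007 | 0.009 | −0.024 | 0.005 |
| 0.5 | −0.001 | 0.000 | −0.052 | −0.003 |

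The simulation error is about 0.117/√600 = 0.005. With the same loss pattern in both arms, round makes no difference to bias. With crossed loss, including it removes the bias to within simulation error.

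**5. Precision.** With equal rounds, round explains g²/4 divided by 1.9². For g = 0.1 this is 0.07%, and for g = 0.5 it is 1.7%. The 228 becomes 227.8 to 224.1.

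**6. Scale.** After 25% loss, 700 × 0.75 = 525 per arm, and the standard error of the contrast is 1.9 × √(2/525) = 0.117. A bias of 0.0125–0.05 is about 0.1–0.4 standard errors.

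**The case against.** **Randomisation already deals with this.** If 1:1 was kept within rounds, round mix is balanced by design. If simple randomisation was used, any imbalance is chance, and the ordinary standard error covers it. With equal rounds, the standard error of the arm difference in round share is √(0.25 × 2/700) = 0.027. Five points is then about 1.9 standard errors and ten about 3.7. Nothing in the documents suggests that the ratio differed by round. This stands, and it is why the expected bias may well be zero. However, the within-round ratio is not reported. SAP 2.2 also removes patients found ineligible after randomisation (it anticipates at most 5% with such deviations), so exact balance within rounds need not survive.

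**Year-end loss alone does no harm.** A reader might infer that different timing of loss by round biases the comparison in itself. It does not: step 4 shows no bias when both arms share the pattern. Both documents assume non-differential loss, and neither gives a reason to expect crossing. It is also not shown that the rounds differ in total loss, only in its timing and plausibly in which values are observed.

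**The plan has fallbacks.** The conditional adjusted analysis, the complete-case analysis and the longitudinal analysis all help, and Protocol 8.1 promises control of observed imbalance. In the SAP, though, the adjusted analysis is secondary and round is not listed. With equal rounds, a 5-point imbalance is a standardised difference of 0.05/0.5 = 0.10, which only reaches the threshold.

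**Adjustment is not neutral for every outcome.** Odds ratios are non-collapsible, so a round term would change what the planned unadjusted odds ratios estimate. Adherence outcomes are not imputed, so the missing-data argument does not reach them. Both stand, and the fix respects them.

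**Conclusion.** The point holds as a minor specification gap. The two assignment months, the absence of a round term, the absence of any named imputation variable and the silence on within-round allocation are all plain from the documents. Expected bias is zero under 1:1 allocation within rounds and non-differential loss. It is about 0.01–0.05 HbA1c points only under assumed arm differences in round mix or crossed loss. The top of that range needs rounds to differ by 0.5 in mean HbA1c change, as large as the trial's whole target.

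A reader might set 0.05 against 0.5 × 0.30 = 0.15, the diluted effect at the SAP's 30% participation, and call it a third of the effect. The documents do not support that denominator: SAP 1.3 states 0.5 as the difference between the randomised groups, and Protocol 8.2 treats it as an overall difference. Nor do they show that the primary estimate is biased, or that round was a stratification factor.

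Two neighbouring gaps remain whatever is done about round: the imputation model is unspecified as a whole, and the follow-up HbA1c has no window. A round term does not cure the second.

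**What to change.** - In SAP 4.2.1, include assignment round (October or December 2016) as a fixed factor in the GEE for change in HbA1c. With an identity link, this keeps the result as an absolute difference in change.
- In SAP 3.1, name the imputation variables, including round and its interaction with arm.
- Report the size and allocation ratio of each round, and tabulate allocation and missing follow-up HbA1c by round and arm.
- For the binary secondary outcomes, keep the planned unadjusted odds ratio and give a round-adjusted version as a sensitivity analysis.

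The cost is one degree of freedom in the main model, two terms in the imputation model, one table and slightly more analysis. The required sample size is essentially unchanged. The assignment date is needed anyway to start follow-up. SAP 2.2 places transfer of the full data after the late-March 2018 lockout, so the change could be specified before the investigators hold outcome data.

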3. PRIMARY AND SECONDARY VARIABLES

3.1 Primary outcome (mean change in glycemetic control):

The primary outcome of interest will be the pre- to post-intervention change in mean HbA1c levels to the end of the 12-month follow-up period. Follow-up will begin from the date of treatment group assignment. The data for this outcome will be based on laboratory information that Horizon Blue Cross Blue Shield of New Jersey receives from over 200 patient-centered medical homes and other population health programs used for quality improvement monitoring. This laboratory information will be used to measure the change in HbA1c levels at the end of follow-up. In specific, the HbA1c result recorded closest to the 12-month end of follow-up as provided in the laboratory data will be used for the primary analysis.

For subjects with missing outcome data, multiple imputation will be used to impute missing follow-up values to calculate the change in HbA1c levels.¹⁰ Of note, all patients by definition for inclusion in the study will have baseline HbA1c values. This imputation approach is used to generate multiple results for missing values based on the underlying distribution of the available data. We will test the robustness of this approach with sensitivity analyses that use alternative methods of handling missing data, including complete case analysis.

This outcome will be analysed formally. We will also explore any potential differences in effectiveness by the pharmacist delivering the intervention.

3.2 Secondary outcome (proportion achieving glycemic control):

The secondary glycemic outcome will include the proportion of patients achieving optimal glycemic control. Optimal glycemic control will be defined as the proportion of patients who achieved an HbA1c result <8.0% in the 12-month follow-up period. This conservative threshold is based on the minimum threshold that nearly all patients should achieve based on guidelines from the American Diabetes Association (ADA) and quality measures used to assess the performance of health plans.^{11,12} In specific, we will use the laboratory information provided to Horizon and will use the HbA1c result recorded closest to the 12-month end of follow-up for the primary analysis.

For subjects with missing outcome data, we will use multiple imputation to impute missing follow-up values to calculate the proportion of patients who achieved this threshold.

This outcome will be analysed formally.

3.3 Secondary outcome (two medication adherence outcomes):

Medication adherence will be measured using filling patterns in pharmacy claims data for medications that qualified a patient for inclusion in the study.¹³ For each medication, we will create a drug supply diary linking all observed fills after initiation based on dispensing date and days' supply. Different drugs in the same chemically-related therapeutic class (e.g., sulfonylureas) will be considered to be interchangeable. We will allow for up to 180 days of carryover supply. From these supply diaries, we will calculate the proportion of days that patients had medications available to them, or the proportion of days covered (PDC), by dividing the number of days with medication available by the number of days during follow-up.¹⁴ If a patient loses continuous eligibility during the year after the index date, the PDC will be calculated based on the number of days available. If a patient loses continuous eligibility during the year after the index date, they will be censored on that date, and the PDC will be calculated based on the number of days available. In this PDC measurement, if patients had at least one antidiabetic medication available, then they will be considered to be adherent for that day. This definition allows for outcome measurement even when patients switch (e.g., switch from metformin to a sulfonylurea) or intensify therapy (e.g., adding a second oral diabetes medication or injectable medication).

Using this PDC measure, we will observe *1) the mean PDC in each study arm* and *2) the proportion of patients achieving optimal adherence* (defined by ≥ 0.80 PDC) as adherence outcomes in the follow-up period. In a sensitivity analysis of this outcome, medication adherence will be measured by calculating the PDC beginning from the first fill of a medication after assignment until the end of the 12-month follow-up. There will be no missing data for these outcomes, as previously described.

These outcomes will be analysed formally.

3.4 Secondary analyses:

Resource utilization:

As secondary analyses, we will also measure healthcare spending and healthcare resource utilization, including outpatient visits, emergency room visits, and hospitalizations, in the follow-up period in the medical and pharmacy claims data. Healthcare spending will be measured as total allowed amounts in

the 12 months after randomization or until they lose continuous enrolment in both the medical and pharmacy claims files. This spending will sum the insurer paid amounts, coinsurance, copayments, and deductibles paid by patients. Healthcare resource utilization will be measured in the medical claims data. In specific, we will measure the count of outpatient office visits to providers, the count of emergency room visits, and the number of times each patient was hospitalized as outcomes from their randomization date until 12 months after randomization or until they lose continuous enrolment. These outcomes will be analysed formally.

Medication adherence:

Other medication adherence measurements will also be assessed descriptively, including adherence to each individual anti-diabetic medication, the proportion of patients who were adherent (defined by $\geq 80\%$ PDC), and gaps in medication availability. For these definitions, rates of switching, augmentation, discontinuation and other changes in prescription patterns will also be measured descriptively. Adherence to each diabetes medication will be measured using PDC, adjusting the denominator for new medication based on the number of days in the follow-up period that medication was used for. Persistence to medications will also be assessed, defined as a gap in supply of ≥ 60 days following exhaustion of the drug supply in the follow-up period. If insulin is used adjunctively or instead of oral therapy, persistence to insulin will also be measured. This approach to multiple medications has been used in other studies by our study group.^{3,15} These are planned to be measured descriptively.

Uptake of intervention:

We will also descriptively examine the number of follow-up calls and the number of patients who choose each type of decision (e.g., treatment intensification or adherence/lifestyle improvement). This will be based on de-identified call data provided by [REDACTED] (the pharmacists delivering the intervention).

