4. STUDY PLAN AND TIMING OF PROCEDURES

There are no formal visits in this study or any clinical procedures that will be conducted outside of routine care. We will not be requiring patients to seek care at any specified intervals to obtain study data to mimic real-world clinical practice.

The study plan and timing of the study interventions are shown in Table 4 below.

Table 4. Timing of study interventions

Study Arm	Initial mailing	Initial call	Follow-up call (#1)	Follow-up call (#2)	Follow-up call (#3)
Intervention group	Invitation letter	Consent + Introduction + SDM + BNI	Booster: SDM + BNI	Booster: SDM + BNI	Booster: SDM + BNI

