4.2 Treatment period

Patients will be followed from the identification until the end of the study. Patients in the intervention group will be contacted within their first month after identification, initially by mailed communication and then via the telephonic intervention. Follow-up “booster” telephonic phone calls by clinical pharmacists will be used at least 3 more times to support the intervention.

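### The primary HbA1c rule sets no earliest draw date, so a sole result from the first weeks is analysed as an observed 12-month outcome and is not imputed

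*SAP*

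**What the plan says.** SAP 3.1 defines the primary outcome as the "change in mean HbA1c levels to the end of the 12-month follow-up period". To put this into practice it uses "the HbA1c result recorded closest to the 12-month end of follow-up as provided in the laboratory data". The only lower limit on timing is the start of follow-up: "Follow-up will begin from the date of treatment group assignment". For patients without an outcome, "multiple imputation will be used to impute missing follow-up values to calculate the change in HbA1c levels". SAP 3.2 applies the same closest-to-month-12 rule, and the same imputation, to the proportion with HbA1c below 8%.

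Neither document gives an earliest acceptable day, a window around month 12, or a definition of missing that depends on timing. HbA1c tests are not scheduled. Protocol section 4 states: "We will not be requiring patients to seek care at any specified intervals to obtain study data". On the intervention, Protocol 4.2 says "Patients in the intervention group will be contacted within their first month after identification", first by mail and then by telephone, with at least three further calls whose dates are not given.

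SAP 4.2.1 plans two sensitivity analyses for the glycemic outcomes: a complete-case analysis, and longitudinal generalized estimating equations (GEE) that add any other HbA1c values from the 12 months.

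**The concern.** Read as a programmer would read it, the rule selects the latest available result before month 12, however early that is. A single result from week 2 is the closest one to month 12, so it is observed, is not missing, and is not imputed.

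Such patients are foreseeable. Tests follow routine care. SAP 1.3 allows for 25% loss and explains: "Because patients may change insurance, in particular at the end of the calendar year". SAP 2.2 states that all patients were eligible "at the time the assignment was actually performed in Oct 2016 and Dec 2016". A patient whose coverage ended on 31 December 2016 could have at most about three months of laboratory data if assigned in October, and less than one month if assigned in December.

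Three things are at stake:

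- **Dilution.** A value drawn before first contact cannot carry any effect of the intervention. Very early values after contact probably carry little, since SAP 1.3 expects meaningful differences within an 11 to 12-month follow-up.
- **Bypassed imputation.** The plan has a method for patients without a 12-month result, but this rule keeps the early-only patients out of it. SAP 3.1 bases imputation on the distribution of the available data, so early values labelled as 12-month outcomes can also influence what is imputed for others.
- **Draw times by arm.** If the intervention changes when patients are tested, any general trend in HbA1c over time would enter the comparison.

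**Working it through.** **Step 1: follow one patient through the rule.** Assigned on day 0, one HbA1c on day 14, coverage lost afterwards.

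| Analysis | Treatment of the day-14 value |
|---|---|
| Primary (SAP 3.1) | Only follow-up value, hence closest to month 12; used as observed |
| Imputation (SAP 3.1) | Not triggered, as a value exists |
| Complete case (SAP 4.2.1) | Kept as complete |
| Longitudinal GEE (SAP 4.2.1) | No later value to add; no window or time model stated |
| HbA1c below 8% (SAP 3.2) | Same value, same rule |

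**Step 2: reproduce the plan's sample size.** Inputs from Protocol 8.2 and Table 5: difference 0.5, SD 1.9, alpha 0.05 (two-sided in SAP 4.1), power 0.80, clustering factor 1.03, loss 25%, contact rate 45%.

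- Base: n = 2 × (1.96 + 0.8416)² × 1.9² / 0.5² = 226.7, so 227. The t-test version gives 227.6, so 228 as in Table 5.
- 228 × 1.03 = 235; 235 / 0.75 = 313.3; 313.3 / 0.45 = 696, as stated.

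The planned 80% power therefore rests on a difference of 0.5 with about 228 evaluable patients per arm. It corresponds to a standardised effect (difference divided by its standard error) of 1.96 + 0.8416 = 2.80.

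**Step 3: effect of early values.** Let f be the share of analysed values that are too early. This is an assumption, and the range is illustrative.

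- *Rule as written, early values carry no effect:* the difference is 0.5 × (1-f), and power = Φ(2.80 × (1-f) - 1.96).
- *Same patients treated as missing, no gain from auxiliary data:* the difference stays 0.5 but the information falls to (1-f), so power = Φ(2.80 × √(1-f) - 1.96).
- *Rule as written, early values carry half the effect:* power = Φ(2.80 × (1-f/2) - 1.96).

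| f | Difference, no early effect | Power, rule as written | Power, treated as missing | Power, rule, half effect |
|---|---|---|---|---|
| 0 | 0.500 | 80% | 80% | 80% |
| 5% | 0.475 | 76% | 78% | 78% |
| 10% | 0.450 | 71% | 76% | 76% |
| 20% | 0.400 | 61% | 71% | 71% |
| 30% | 0.350 | 50% | 65% | 66% |

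The net cost of the rule is the gap between the third and fourth columns: about 5 points at f=10% and 10 points at f=20%. The matching sample-size ratio is (1-f)/(1-f)² = 1/(1-f), that is 1.11 and 1.25.

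**Step 4: a second way to count.** If the early-only patients come from the 25% already written off as lost, the rule adds them back: N rises by 1/(1-f) while the difference falls to (1-f). The standardised effect is then 2.80 × √(1-f), giving 76% at f=10% and 71% at f=20%, against 80% when they are left out. The gap is again about 4 to 5 and 9 to 10 points.

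**The case against.** The strongest reply is that the rule uses an early value only when no later one exists, that the SAP states its aim as change to the end of 12 months, and that missing is undefined, so an analyst might send such patients to imputation anyway. The longitudinal analysis also probes timing. What stands is that the intent is clear. But an aim is not a limit that can be programmed, and the longitudinal model has nothing to add for a patient with no later value. The documents do set limits elsewhere: 180 days for the qualifying HbA1c, 180 days of carryover supply, and a 60-day gap for persistence.

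A second reply is that the remedy also costs precision. This stands, and is why step 3 compares the rule with its alternative and not with 80%. If early values carry about half the effect, power is much the same either way; the estimate is still a diluted version of the 12-month difference.

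A reader might also infer stronger points, which the documents do not support:

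- *That the 25% loss indicates f, being mostly year-end insurance changes.* SAP 1.3 singles out year-end changes without saying that they are the majority, and also mentions patients with no follow-up HbA1c. Someone who leaves within weeks may have no post-assignment result at all, and would be imputed as planned.
- *That early values cannot reflect the intervention.* This is certain only before first contact. A value at two to three months may follow the mailing and the first call.
- *That unequal draw times produce a bias of known size, large against an intention-to-treat difference of 0.15 (0.5 × 30% participation).* Neither the imbalance nor the time trend is given. The documents do not state 0.15, and it cannot be combined with 80% power: with SD 1.9 and 700 × 0.75 = 525 per arm it gives about 25%.

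**Conclusion.** The gap is real and lies in the stated rule for the primary endpoint and for one secondary endpoint. Followed exactly, it analyses a sole result from the first weeks as a 12-month outcome and keeps that patient out of the imputation. No planned analysis corrects this for a patient without a later value.

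The direction is certain for values drawn before first contact and likely for other very early values. It need not hold for mid-period values if the effect peaks before month 12. The size cannot be fixed, because f is not in the documents. Under the assumption of no effect in early values, and taking the plan's own 80% as the start, the rule costs about 5 points of power at f=10% and 10 points at f=20% relative to treating those patients as missing, and it shrinks the difference from 0.50 to 0.45 or 0.40. Bias from different draw times by arm is possible, but the documents give no basis for sizing it.

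Confidence is high on the wording and modest on the magnitude. The rule should be changed, since the remedy is cheap and the present rule gives a worse estimate of the stated outcome.

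**What to change.** SAP 2.2 places the lock for follow-up outcomes in late March 2018, with data sharing after it. Before then, amend SAP 3.1 and 3.2 as follows:

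1. Accept only HbA1c results drawn at or after a pre-specified minimum time from assignment, and take the one closest to day 365. Ninety days is a workable example; it is an analytic choice, not a figure from the documents. State also whether a result drawn after day 365 may be used.
2. Treat patients with only earlier results as missing, and impute them with the multiple imputation already planned, entering the early results as auxiliary variables in the imputation model.
3. As sensitivity analyses, repeat with a 180-day minimum and with the SAP's present any-value rule.
4. Tabulate the draw time of the analysed value by arm, with the number of patients who have only early results. This supplies f and shows whether timing differs between arms.

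The cost is a few sentences in the SAP, a larger imputed share with more reliance on the imputation model, and slightly wider intervals. The early values as auxiliaries should recover part of that precision. If the minimum is chosen only after the data are seen, it becomes a data-driven change to the primary endpoint.
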